## **8.4 Postoperative Evaluation-Day 28 (± 7D) Visit**

### **8.4.1 Concomitant Medications**

Changes in all concomitant prescription medications and aspirin use will be documented in the source documents and recorded in the eCRF.

### **8.4.2 Symptom-directed Physical Examination, including Temperature**

Perform a symptom-directed PE (if needed) including subject's temperature (at all visits irrespective of symptoms). The investigator or qualified medical personnel who routinely perform these evaluations in this patient population will conduct the examination, determine findings, and assess any abnormalities with respect to clinical significance.

### **8.4.3 Assessment of Surgical Site Healing**

A clinical examination of the surgical site should be conducted and the findings documented in the eCRF.

### **8.4.4 Clinical Examination of the Access Site and HAV**

A clinical examination of the access site and HAV will be performed at all postoperative study visits.

#### **8.4.5 Assessment of any Problems with Access Site or HAV and HAV Interventions**

Any problems and interventions with the access site and HAV including infections and the occurrence of thrombosis must be documented. Any procedures performed or treatments, including reasons for the procedures and dates of hospitalization, will be documented in the source documents and recorded in the eCRF.

#### **8.4.6 Assessment of HAV Patency**

The patency of the HAV and adequacy of flow will be assessed by the investigator using the investigator's preferred method (eg. palpation, stethoscope auscultation, Doppler, ultrasound, etc.).

#### **8.4.7 Duplex Ultrasound**

A duplex ultrasound will be performed to assess HAV patency, diameter of the lumen mid-conduit, implant and anastomotic stenosis, volumetric flow rate, and to monitor for true aneurysm development. The full length of the HAV should be visualized with particular attention paid to any increase in diameter of the conduit that might indicate aneurysm formation. For purposes of this study, the full length of the HAV constitutes the entire conduit and includes both arterial and venous anastomoses. The methodology will be described in the study manual.

#### **8.4.8 Determination that the HAV may be used for Dialysis**

Beginning on Day 28 post-implantation ( $\pm 7$  days), the investigator (or designee) should evaluate the HAV to determine if it is suitable to be used for dialysis. Such suitability will be recorded in the eCRF and transmitted to the dialysis center caring for that subject with guidance that cannulation of the HAV for dialysis should not start before 28 days post-implantation (earlier use of the HAV for dialysis for urgent clinical reasons may be permitted but must be approved prospectively by the medical monitor).

If the HAV is deemed not ready for use, either the subject should be brought back to the site for a repeat assessment in a few weeks, or an intervention arranged.

#### **8.4.9 Assessment of Hemodialysis and Placement and/or Removal of Central Venous Catheter**

Information on subject hemodialysis since the last study visit, including frequency will be documented in the source documents and recorded in the eCRF. Additionally, information on CVC in place or if the subject had a CVC in place since the last visit will be documented in the source documents and recorded in the eCRF. Of particular interest is whether an alternate route for dialysis (CVC, peritoneal) is used and for how long.

#### **8.4.10 Assessment of Adverse Events**

The subject will be asked general questions about his/her health and for any HAV or dialysis problems since the previous visit. See [Section 9](#) for information regarding AE collection and data handling.

#### **8.4.11 Assessment of Events of Special Interest**

Subjects should be assessed for the occurrence of Events of Special Interest as defined in [Section 9.3](#). Detailed information about each of these events will be recorded in the eCRF as described in [Section 8.3.9](#).

#### **8.4.12 Laboratory Evaluations**

At Day 28 ( $\pm 7$  days), a blood sample will be collected for the following:

- Hematology: hemoglobin, hematocrit, RBC, WBC with differential, platelet count.
- Clinical chemistry: sodium, potassium, calcium, BUN or urea, creatinine, albumin, total bilirubin, glucose (non-fasting).
- PRA
- Anti-HAV IgG antibodies

### **8.5 Postoperative Evaluations (Month 2 to Month 12)**

#### **8.5.1 Evaluations and Procedures to be performed at All Study Visits from Month 2 to Month 12**

The following assessments will be performed at the Month 2 ( $\pm 7$  days), Month 3 ( $\pm 7$  days), Month 6 ( $\pm 14$  days), and 12 ( $\pm 14$  days), visits:

##### **8.5.1.1 Concomitant Medications**

All concomitant prescription medications and aspirin taken during the study up to Month 12 will be recorded in the eCRF.

##### **8.5.1.2 Symptom-directed Physical Examination, including Temperature**

Perform a symptom-directed PE (if needed) including subject's temperature (at all visits irrespective of symptoms). The investigator or qualified medical personnel who routinely perform these evaluations in this patient population will conduct the examination, determine findings, and assess any abnormalities with respect to clinical significance.

### **8.5.1.3 Clinical Examination of the Access Site and HAV**

A clinical examination of the access site and HAV will be performed at all postoperative study visits.

### **8.5.1.4 Assessment of HAV Patency**

The patency of the HAV and adequacy of flow will be assessed by the investigator using the investigator's preferred method (eg. PE[ie. palpation, stethoscope auscultation], Doppler exam, ultrasound imaging, etc.).

### **8.5.1.5 Assessment of any Problems with the Access Site and HAV and Interventions, Including Events of Special Interest**

Any problems and interventions with the access site and HAV including infections and the occurrence of thrombosis must be documented. Any procedures performed or treatments, including reasons for the procedures and dates of hospitalization, will be documented in the source documents and recorded in the eCRF.

Subjects should be assessed for the occurrence of Events of Special Interest as defined in [Section 9.3](#). Detailed information about each of these events will be recorded in the eCRF as described in [Section 8.3.9](#). If the HAV is abandoned, the reason for abandonment will be documented in the eCRF.

### **8.5.1.6 Duplex Ultrasound**

A duplex ultrasound will be performed to assess HAV patency, diameter of the lumen mid-conduit, implant and anastomotic stenosis, volumetric flow rate, and to monitor for aneurysm development. The full length of the HAV should be visualized with particular attention paid to any increase in diameter of the HAV that might indicate aneurysm formation.

### **8.5.1.7 Determination that the HAV may be used for Dialysis (if not previously approved)**

The investigator should evaluate the HAV to determine if it is suitable to be used for dialysis. Such suitability will be recorded in the eCRF and transmitted to the dialysis center caring for that subject with guidance that cannulation of the HAV for dialysis should not start before 28 days post-implantation.

### **8.5.1.8 Assessment of Hemodialysis and Placement and/or Removal of CVC**

Information if the subject underwent hemodialysis since the last study visit, including frequency will be documented in the source documents and recorded in the eCRF. Additionally, information if the subject has a CVC in place or if the subject had a CVC in place since the last

visit will be documented in the source documents and recorded in the eCRF. Of interest is whether an alternate route for dialysis (CVC, peritoneal) is used and for how long.

#### **8.5.1.9 Assessment of Adverse Events**

The subject will be asked general questions about his/her health and for any HAV or dialysis problems since the previous visit. See [Section 9](#) for information regarding AE collection and data handling.

### **8.5.2 Evaluations and Procedures to be performed only at Specific Visits from Month 2 to Month 12**

#### **8.5.2.1 Removal of CVC that was in place Pre-implantation: Month 2 and 3**

The date and reason for removal of the CVC that was in place pre-implantation, if applicable, will be documented in source data and recorded in eCRF.

#### **8.5.2.2 PRA and Anti-HAV IgG Antibodies: Month 2, 6, and 12**

A blood sample will be collected for the PRA and Anti-HAV IgG antibodies evaluation.

#### **8.5.2.3 Laboratory Data: Month 2**

At Month 3 a blood sample will be collected for the following:

- Hematology: hemoglobin, hematocrit, RBC, WBC with differential, platelet count.
- Clinical chemistry: sodium, potassium, calcium, BUN or urea, creatinine, albumin, total bilirubin, glucose (non-fasting)

## **8.6 Long Term Follow Up Post Month 12 through Month 36 Evaluations and Procedures**

After 12 months, only subjects with a patent HAV will be followed for up to 3 years (36 months) post-implantation at study visits every 6 months.

### **8.6.1 Evaluations and Procedures that will be performed at All Study Visits Post Month 12 to Month 36 ( $\pm$ 1M)**

#### **8.6.1.1 Symptom-directed Physical Examination, including Temperature**

Perform a symptom-directed PE (if needed) including subject's temperature (at all visits irrespective of symptoms). The investigator or qualified medical personnel who routinely perform

these evaluations in this patient population will conduct the examination, determine findings, and assess any abnormalities with respect to clinical significance.

#### **8.6.1.2 Clinical Examination of Access Site and HAV**

A clinical examination of the access site and HAV will be performed at all post Month 12 study visits.

#### **8.6.1.3 Assessment of HAV Patency**

The patency of the HAV and adequacy of flow will be assessed by the investigator using the investigator's preferred method (eg. palpation, stethoscope auscultation, Doppler exam, ultrasound imaging, etc.). This assessment is not required for HAV that have been abandoned.

#### **8.6.1.4 Assessment of any Problems with the Access Site or HAV and Interventions, Including Events of Special Interest**

Any problems and interventions with the access site and HAV including infections and the occurrence of thrombosis must be documented. Any procedures performed or treatments, including reasons for the procedures and dates of hospitalization, will be documented in the source documents and recorded in the eCRF.

Subjects should be assessed for the occurrence of Events of Special Interest as defined in [Section 9.3](#). Detailed information about each of these events will be recorded in the eCRF as described in [Section 8.3.9](#). If the HAV is abandoned, the reason for abandonment will be documented in the eCRF.

#### **8.6.1.5 Determination that the HAV may be used for Dialysis (if not previously approved)**

The investigator should evaluate the HAV to determine if it is suitable to be used for dialysis. Such suitability needs to be recorded in the eCRF and transmitted to the dialysis center caring for that subject.

#### **8.6.1.6 Assessment of Hemodialysis and Placement and/or Removal of CVC**

Information if the subject underwent hemodialysis since the last study visit, including frequency will be documented in the source documents and recorded in the eCRF. Additionally, information if the subject has a CVC in place or if the subject had a CVC in place since the last visit will be documented in the source documents and recorded in the eCRF. Of particular interest is whether an alternate route for dialysis (CVC, peritoneal) is used and for how long.

#### **8.6.1.7 Duplex Ultrasound**

A duplex ultrasound will be performed to assess HAV patency, diameter of the lumen mid-conduit, implant and anastomotic stenosis, volumetric flow rate, and to monitor for aneurysm development. The full length of the HAV should be visualized with particular attention paid to any increase in diameter of the HAV that might indicate aneurysm formation.

### **8.7 Early Termination Visit**

If a subject discontinues from the study before the Month 36 visit, then every effort should be made to perform the following early termination (ET) visit assessments:

- Patients withdrawn prior to Month 12 should complete an ET that correlates with the procedures at Month 12.
- Patients withdrawn after Month 12 and prior to Month 36 should complete an ET visit that correlates with procedures post Month 12 through Month 36.

#### **8.7.1 Concomitant Medications (if prior to month 12)**

Any changes to the subject's prescription medications and aspirin use will be documented in source data and recorded in eCRF.

#### **8.7.2 Symptom-directed Physical Examination, including Temperature**

Perform a symptom-directed PE (if needed) including subject's temperature (at all visits irrespective of symptoms. The investigator or qualified medical personnel who routinely perform these evaluations in this patient population will conduct the examination, determine findings, and assess any abnormalities with respect to clinical significance.

#### **8.7.3 Clinical Examination of the Access Site and HAV**

A clinical examination of the access site and HAV will be performed.

#### **8.7.4 Assessment of HAV Patency**

The patency of the HAV and adequacy of flow will be assessed by the investigator using the investigator's preferred method (eg. palpation, stethoscope auscultation, Doppler, ultrasound, etc.).

#### **8.7.5 Assessment of any Problems with the Access Site or HAV and Interventions, Including Events of Special Interest**

Any problems and interventions with the access site and HAV including infections and the occurrence of thrombosis must be documented. Any procedures performed or treatments, including reasons for the procedures and dates of hospitalization, will be documented in the

source documents and recorded in the eCRF. Subjects should be assessed for the occurrence of Events of Special Interest as defined in [Section 9.3](#). Detailed information about each of these events will be recorded in the eCRF as described in [Section 8.3.9](#). If the HAV is abandoned, the reason for the abandonment will be documented in the eCRF.

### **8.7.6 Duplex Ultrasound**

A duplex ultrasound should be performed to assess HAV patency, diameter of the lumen mid-conduit, implant and anastomotic stenosis, volumetric flow rate, and to monitor for aneurysm development. The full length of the HAV should be visualized with particular attention paid to any increase in diameter of the HAV that might indicate aneurysm formation.

### **8.7.7 Assessment of Hemodialysis and Placement and/or Removal of Central Venous Catheter**

Information if the subject underwent hemodialysis since the last study visit, including frequency will be documented in the source documents and recorded in the eCRF. Additionally, information if the subject has a CVC in place or if the subject had a CVC in place since the last visit will be documented in the source documents and recorded in the eCRF. Of particular interest is whether an alternate route for dialysis (CVC, peritoneal) is used and for how long.

### **8.7.8 Assessment of Adverse Events**

The subject will be asked general questions about his/her health and for any HAV or dialysis problems since the previous visit. See [Section 9](#) for information regarding AE collection and data handling.

### **8.7.9 PRA and Anti-HAV IgG Antibodies (if prior to month 12)**

A blood sample to measure PRA and anti-HAV IgG antibody levels must be collected.

## **8.8 Collection and Processing of Laboratory Samples**

Details concerning sample collection and processing can be found in the Study Manual.

## 9. SAFETY ASSESSMENTS AND ADVERSE EVENTS

The safety of the HAV will be assessed in terms of the following:

- Anastomotic rupture
- Anastomotic bleeding
- HAV spontaneous rupture
- Aneurysm
- Pseudoaneurysm
- HAV infection
- Increase from baseline in PRA/Anti-HAV IgG antibodies
- Need for HAV revision or removal
- Other AEs
- Laboratory parameters (clinical chemistry and hematology)

### 9.1 Definition of Adverse Events

An AE is defined as any untoward medical occurrence in a subject administered an IMP or has undergone study procedures and which does not necessarily have a causal relationship with this treatment. An AE can therefore be any unintended sign (including an abnormal laboratory finding), symptom, or disease temporally associated with the use of the IMP, whether or not related to the IMP.

An abnormality identified during a medical test (e.g., laboratory parameter, vital sign, ECG data, PE) should be defined as an AE only if the abnormality meets 1 of the following criteria:

- Induces clinical signs or symptoms
- Requires active intervention
- Requires removal or abandonment of the HAV
- The abnormality or test result is clinically significant in the opinion of the investigator.

### 9.2 Definition of Serious Adverse Events

An AE is considered “serious” if, in the view of either the investigator or Sponsor, it:

- Results in death.
- Is life threatening (An AE is considered “life-threatening” if, in the view of either the investigator or Sponsor, its occurrence places the subject at immediate risk of death. It does not include an adverse event that, had it occurred in a more severe form, might have caused death).
- Results in persistent or significant disability/incapacity or substantial disruption of the ability to conduct normal life functions.

- Results in congenital anomaly or birth defect.
- Requires inpatient hospitalization or leads to prolongation of hospitalization (hospitalization for treatment/observation/examination caused by AE is to be considered as serious).
- Represents a medically important event as determined by the investigator.

Medical and scientific judgment should be exercised in deciding whether AEs are serious, such as important medical events that may not be immediately life-threatening or result in death or hospitalization but may jeopardize the subject and may require medical or surgical intervention to prevent one of the other outcomes listed in the definition above. These events, including those that may result in disability/incapacity, should also usually be considered serious. Examples of such events are intensive treatment in an emergency room or at home for allergic bronchospasm; blood dyscrasias or convulsions that do not result in hospitalization; or development of drug dependency or drug abuse.

Note: Hospitalization for the surgical placement of the HAV will not be considered an SAE. However, prolongation of the initial hospitalization due to an AE will be considered a SAE.

### **9.2.1 Suspected Unexpected Serious Adverse Reactions**

A suspected unexpected serious adverse reaction (SUSAR) is any adverse drug reaction that is serious, unexpected and suspected, meaning there is a reasonable possibility that the IMP caused the adverse event. An AE or suspected adverse reaction is considered "unexpected" if it is not listed in the Investigator Brochure or is not listed at the specificity or severity that has been observed.

### **9.3 Events of Special Interest**

Events of Special Interest related to interventions and infections will be evaluated and include the following:

- Events resulting in HAV abandonment
- HAV thrombosis
- HAV infection
- HAV aneurysm (HAV lumen diameter > 9 mm ) formation
- Clinically significant HAV pseudoaneurysm (clinically significant defined as requiring a surgical or radiological intervention)
- HAV spontaneous rupture
  - Iatrogenic injuries are not an Event of Special Interest and should be reported as an AE
- Events resulting in HAV revision or ligation

- Events resulting in HAV removal
- Clinically significant stenosis of HAV (clinically significant defined as severity of severe or greater, or requiring a surgical or radiological intervention)
- Clinically significant Steal Syndrome (clinically significant defined as severity of severe or greater, or requiring a surgical or radiological intervention)
- Anastomotic bleeding
- Anastomotic rupture

## 9.4 Criteria for Determining Causal Relationship to the HAV and Criteria for Determining Casual Relationship to Index Surgical Procedure

The criteria for determining the causal relationship of an AE with the HAV is presented in the table below. A separate assessment of causal relationship of an AE to the HAV implantation procedure is required as well using the same criteria and definitions presented in the table below. Please note that causal relationship to procedure only refers to the index surgical procedure in which the HAV was initially implanted.

Causal Relationship to the HAV	Criteria for Determining Causal Relationship
Definitely Related	There is clear evidence to suggest a causal relationship, and other possible contributing factors can be ruled out. The clinical event, including an abnormal laboratory test result, occurs in a plausible time relationship to placement of the HAV and cannot be explained by concurrent disease or other devices, drugs, or chemicals.
Possibly Related	There is some evidence to suggest a causal relationship (e.g., the event occurred within a reasonable time after the placement of the HAV). However, the influence of other factors may have contributed to the event (e.g., the subject's clinical condition, other concomitant events). Although an adverse effect may rate only as "possible" soon after discovery, it can be flagged as requiring more information and later be upgraded to probable or certain as appropriate.
Unlikely Related	A clinical event, including an abnormal laboratory test result, whose temporal relationship makes a causal relationship improbable (e.g., the event did not occur within a reasonable time after placement of the HAV) and in which other drugs or chemicals or underlying disease provide plausible explanations (e.g., the subject's clinical condition, other concomitant treatments).
Not Related	A clinical event, including an abnormal laboratory test result, which occurs when the subject was not exposed to the HAV or, another cause is obvious and in which there is sufficient information that the etiology of the event is not related to the HAV.

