## **2.4 Study Design Rationale**

Previous studies with the HAV have used IMP manufactured using small-scale systems (Aura and Terra). Prior to commercialisation, manufacturing has been switched to a larger-scale automated process with greater in-process controls (Luna). Based on a large number of preclinical parameters, including those used for batch release, the IMP manufactured using the Luna system is comparable to that used in earlier clinical studies. This study will allow confirmation of the short-term safety, efficacy and absence of immunogenicity of the Luna product.

Any significant safety or immunogenicity concerns with the HAV would likely be apparent in a short time frame after implant. Thus, the initial study analysis will be conducted after all subjects have reached 3 months post-implant. However, all subjects will be followed for 12 months and those with a patent HAV will continue follow up to 36 months to monitor for any potential long-term safety concerns with the Luna product.

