## **2.5 Potential Risks and Benefits**

### **2.5.1 Potential Risks**

It is anticipated that subjects participating in the study will be exposed to the same risks as those associated with AV graft implantation (some of which have been reported in Phase 2 trial with the HAV – see Investigator Brochure). Risks associated with the HAV may include, but are not limited to, the following:

- Aneurysm or pseudo-aneurysm formation
- HAV rupture
- Bleeding and hematoma formation at the surgical site or the dialysis puncture sites
- Thrombosis/occlusion of the HAV or host vessels

- Stenosis of the HAV or its anastomoses
- Infection of the HAV, at the surgical site or a systemic infection
- Skin erosion
- Steal syndrome and/or high output cardiac failure
- Swelling of the limb

The risks anticipated in this study are similar to those associated with currently marketed prosthetic grafts used for dialysis access. There has been 1 reported aneurysmal dilatation of the HAV in Phase 2. The superficial site of implantation of the HAV facilitates clinical and regular ultrasound monitoring, allowing any such complication to be recognized and treated promptly, and thus minimizing potential risk to the subject.

The HAV is grown using donor human aortic smooth muscle cells. The HAV is decellularized during manufacturing and thus consists of only human ECM proteins. It is possible that the HAV may provoke an immune response which may lead to damage of the HAV and possible cross reactivity against host proteins. Antibody formation will be assessed by monitoring of PRA levels.

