## 9.6 Reporting of Adverse Events

At each evaluation, the subject will be questioned in a general way and no specific symptoms will be suggested. If any AEs have occurred, they will be recorded on the AE pages of the eCRF and in the subject's medical record. If known, the diagnosis should be recorded in preference to the listing of individual signs and symptoms.

During the Screening period (Day -45 to Day 0 prior to implantation), only SAEs related to study procedures will be reported beginning at the time the subject signs the informed consent form. From Day 0 after implantation to 1 year post-implantation (Month 12 visit) or ET visit, whichever occurs earlier, all AEs will be reported.

During the long-term follow-up period from 1 year to 3 years post-implantation, only the following will be reported by the investigator:

- All related SAEs
- All Events of Special Interest (as defined in [Section 9.3](#)).

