3: If adequate vessel mapping has been undertaken within the 8 weeks prior to the start of Screening and there has been no significant change in the condition of the subject (including insertion of CVC) then repeat vessel mapping is at the discretion of the Principal Investigator. Vessel mapping performed by ultrasound in the clinic by the investigator is acceptable.

4: After review by the Principal Investigator, the subject's Screening eCRFs will be provided to the Medical Monitor for review and confirmation of eligibility prior to implantation.

5: Labs include hematology and chemistry. Screening labs will also include INR (or PT if INR value not available) and a serum or urine pregnancy dipstick test for women of childbearing potential. Standard of care laboratory evaluations conducted prior to consent may be used for determination of eligibility provided they are within the screening period time window.

6: Intraoperatively or immediately post-surgery and at Day 7-15, the investigator should use his/her preferred method to confirm patency and adequate flow in the HAV. At all other timepoints, duplex ultrasound will be used to assess patency, diameter of the lumen mid-conduit and flow rate and to monitor aneurysm development. After Month 12, a duplex ultrasound is to be performed at Month 24 and 36.

7: Beginning on Day 28, the investigator may evaluate the HAV to determine if it is suitable to be used for dialysis.

8: Only SAEs related to the screening procedures will be reported during the Screening period. All AEs will be reported from Day 0 after implantation up to the Month 12 visit. After the Month 12 visit up to Month 36, only the following will be reported by the investigator:

- All SAEs considered related to the HAV
- All Events of Special Interest.

9: Subjects will be assessed at a study visit that can occur anytime from Day 7 to 15.

10: Subjects withdrawn prior to the Month 36 visit will have ET assessments performed. Patients withdrawn prior to Month 12 should complete an ET that correlates with the procedures at Month 12. Patients withdrawn after Month 12 and prior to Month 36 should complete an ET visit that correlates with procedures post Month 12 through Month 36.

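### Section 9.4 times relatedness to the HAV from its placement, and after Month 12 that grade decides whether an SAE outside the special-interest list is reported

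*Protocol*

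**What the plan says.** Protocol Section 9.4 gives four grades of causal relationship and applies the same table to the HAV and, in a separate assessment, to the index implantation procedure. Three grades carry a timing criterion, each counted from placement:

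- Definitely Related: the event "occurs in a plausible time relationship to placement of the HAV".
- Possibly Related: "e.g., the event occurred within a reasonable time after the placement of the HAV".
- Unlikely Related: "e.g., the event did not occur within a reasonable time after placement of the HAV". This grade also needs a plausible alternative cause, which may be underlying disease.

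Only Not Related refers to whether the subject was exposed. What counts as a reasonable time is not defined.

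Until Month 12 all AEs are reported. From Month 12 to Month 36, Protocol Section 9.6 restricts reporting to two categories: "All related SAEs" and all Events of Special Interest. Appendix 1, note 8 words the first as "All SAEs considered related to the HAV". SAP Section 7.2 repeats the restriction. Section 2.4 gives the purpose of this late follow-up: "to monitor for any potential long-term safety concerns with the Luna product".

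**The concern.** Surgery is a single past event, so time elapsed since it is a sensible test of whether it caused something. The HAV is a continuing exposure. SAP Section 3.2.4 says it remains in place unless explanted, and SAP Section 7.1 counts exposure from implant to explant. A subject with an HAV at Month 24 is as exposed as at Month 1, yet the table's timing criterion treats that exposure as remote.

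Before Month 12 this matters little: every SAE is reported and a doubtful grade can be revisited. After Month 12, for an SAE not listed in Section 9.3, the grade decides whether it is reported at all. The sponsor's frequency monitoring of unrelated SAEs (Section 9.6.2) can act only on SAEs that reach it. At stake is whether the follow-up meant to detect late safety problems can show those that are systemic and easily attributed to renal disease.

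**Working it through.** There is no figure in the plan to reproduce. The check sets the passages side by side and then sizes the period concerned.

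**1. What Unlikely Related requires.** Two conditions joined by *and*: a temporal relationship that makes causation improbable, and a plausible alternative explanation. For an SAE at Month 24, the only timing guidance offered is the interval since placement. For the second condition underlying disease suffices, and Section 9.6.2 says ESRD patients typically have many SAEs from comorbidities. Both conditions can therefore be met for a late event in a currently exposed subject.

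**2. Which late SAEs depend on the grade.** The risks in Protocol Section 2.5.1, compared with Section 9.3 (reported whatever the causality) and Section 8.6.1.4 (access-site and HAV problems, treatments and hospitalization dates entered in the eCRF at each late visit):

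| Risk in 2.5.1 | On the 9.3 list? | Documented under 8.6.1.4? |
|---|---|---|
| Aneurysm, HAV rupture, HAV thrombosis | Yes (rupture if spontaneous) | Yes |
| Pseudoaneurysm, HAV stenosis, steal | If clinically significant | Largely |
| HAV infection | Yes | Yes |
| Systemic infection without HAV infection | No | Not as such |
| High output cardiac failure | No | Not as such |
| Skin erosion, limb swelling, puncture-site bleeding or hematoma | No | Largely, as local problems |

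Section 2.5.1 lists "Steal syndrome and/or high output cardiac failure" as one item; only clinically significant steal is in Section 9.3. Any event that leads to abandonment, revision, ligation or removal also enters Section 9.3 by that route.

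Abnormal post-cannulation hemostasis belongs to the 36-month safety endpoint (Section 4.2.1.2) but is absent from Section 9.3. A serious late case would be documented as an access-site problem but counted as an SAE only if graded related.

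**3. How much follow-up falls under the filter.** Inputs: 30 subjects (Protocol Summary) and secondary patency of 97%, 91% and 77% at 6, 12 and 24 months in the earlier dialysis studies (Section 2.3.2.1). Assumption: the Month 12–24 hazard continues, so patency at Month 36 = 0.77 × 0.77/0.91 = 0.652.

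With a constant hazard in each interval, h = ln(S_start/S_end)/length, and patent HAV-years = 30 × (S_start − S_end)/h:

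- 0–6 months: h = ln(1/0.97)/0.5 = 0.0609; 30 × 0.03/0.0609 = 14.8
- 6–12 months: h = ln(0.97/0.91)/0.5 = 0.1277; 30 × 0.06/0.1277 = 14.1
- 12–24 months: h = ln(0.91/0.77) = 0.1671; 30 × 0.14/0.1671 = 25.1
- 24–36 months: h = 0.1671; 30 × (0.77 − 0.652)/0.1671 = 21.3 (unrounded patency)

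Totals: 28.9 years before Month 12 and 46.4 after; 46.4/75.3 = 62%.

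Next, add an assumed death rate m. Each interval, starting at year a, becomes 30 × S_start × e^(−m·a) × (1 − e^(−(h+m)·length))/(h+m). The earlier studies' 15 deaths in more than 150 years of follow-up suggest at most about 15/150 = 10% per year.

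| m per year | Before Month 12 | After Month 12 | Share after |
|---|---|---|---|
| 5% | 28.2 | 42.1 | 60% |
| 10% | 27.5 | 38.3 | 58% |
| 15% | 26.8 | 34.8 | 56% |

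A cruder check counts all 30 subjects in Year 1, since they are followed regardless of patency, and uses straight lines afterwards. With Month 36 patency of 50%: 30 × (0.91 + 0.77)/2 + 30 × (0.77 + 0.50)/2 = 44.2, a share of 44.2/74.2 = 60%. With 77%: 48.3/78.3 = 62%. At 10% annual mortality the same method gives 56% to 58%.

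**The case against.** The strongest reply is that the plan already captures most of what matters. A reader might infer that only related SAEs are reported after Month 12. That is not so: all Events of Special Interest are reported with no causality condition, and they cover nearly every way the conduit itself can fail. Sections 8.6.1.2 and 8.6.1.4 add an access-site examination and documentation of problems at every late visit, and SAP Section 7.7 lists access-site and intervention data. It would therefore be wrong to say that late local events disappear from the database. This stands, and it confines the point to SAEs that are not on the Section 9.3 list and not fully captured as access-site or HAV problems.

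Second, a reader might infer that elapsed time forces a late event into Unlikely Related, or that the table biases investigators. The documents do not show this. Under Possibly and Unlikely the interval is only an example, an alternative cause is also required, and no upper limit is set on a reasonable time. How investigators would grade is a prediction. What stands is that the wording permits the outcome and offers no other timing guidance.

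Third, restricting late SAEs to those associated with the HAV is a declared endpoint choice (Section 4.2.1.2). That is fair, and the filter is not disputed here. A filter that rests on causality, however, needs a causality criterion suited to the exposure.

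Fourth, nearly everyone followed after Month 12 has a patent HAV, so an exposure criterion is almost always met and separates little. That is true. The judgement then rests on mechanism and alternative causes, which remain subjective, but elapsed time no longer counts against relatedness by itself.

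**Conclusion.** The point holds in a limited form. For SAEs outside Section 9.3 after Month 12, reporting depends on a grade whose timing criterion runs from placement although exposure is continuing. Such an SAE may be graded Unlikely Related when comorbidity offers an explanation, and then be absent from SAE reporting and tabulation and out of reach of the Section 9.6.2 monitoring. The clearest cases are high output cardiac failure and systemic infection without HAV infection.

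The number of SAEs affected cannot be derived, because the documents give neither a late SAE rate nor a distribution of causality grades. The 56% to 62% is the share of patent HAV-years in the filtered period. It should not be read as a rate of misclassification, and it includes events captured by other routes. It assumes that Luna vessels keep the patency of the earlier ones, that the Month 12–24 hazard continues, and that annual mortality is 0 to 15%. It does not depend on the number of subjects.

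**What to change.** In Protocol Section 9.4, keep time since placement as the timing criterion for the index procedure only. For the HAV, base it on continuing exposure (HAV in place or in use for dialysis) together with compatibility with a known or plausible HAV effect. State that elapsed time since implantation alone does not support Unlikely Related while the HAV is in place.

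Two accompanying edits are worth making at the same time. The Possibly Related row allows an upgrade to probable or certain, which are not on the four-level scale; align it. Neither document says which grades count as related, so state this (for example, Possibly or Definitely Related) in Protocol Sections 9.6 and 9.6.1, in Appendix 1 note 8, and in SAP Section 7.2.5, which tabulates related serious events without a cut-off.

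The cost is protocol wording, eCRF completion guidance and one SAP sentence. The downside is that somewhat more SAEs will be classed as possibly related, so the related-SAE table will look slightly less favourable.
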